### 3. OBJECTIVE(S) AND ENDPOINT(S)

| Objectives   | Endpoints  |
|--|--|
| Primary   |  |
| To assess the utility of a BPE/BPO screening tool in conjunction with PSA in finding men confirmed to have BPH on full urologist assessment of diagnostic test results.  | Proportion of men that are confirmed to have BPH based on full urologist assessment of diagnostic test results among men with a positive result on the BPE/BPO screening tool and tool (score $\geq 3$ ) and serum PSA $\geq 2$ ng/mL.   |
| Secondary   |  |
| 
 
• To assess the utility of a BPE/BPO screening tool in conjunction with PSA in finding men with risk of BPH Progression on full urologist assessment of diagnostic test results.
 
• To assess the utility of a BPE/BPO screening tool in finding men diagnosed with probable BPH as assessed by the GP.
 
• Compare the utility of the BPE/BPO screening tool with the IPSS screening tool.
 
 | 
 
• Proportion of men that are confirmed to be a risk for BPH progression based upon full urologist assessment among men with a positive result on the BPE/BPO screening tool and probable GP BPH diagnosis.
 
• Proportion of men that are diagnosed with probable BPH as assessed by the GP among men with a positive result on the BPE/BPO screening tool (score <math>\geq 3</math>).
 
• Agreement (using Kappa statistic for categories) between the BPE/BPO screening tool assessment (score <math>\geq 3</math>) and an IPSS score approach (score <math>\geq 8</math>) in selecting men to investigate for BPH.
 
 |
|  Probable BPH is the presumptive diagnosis of urinary tract obstruction from an enlarged prostate based on clinical symptoms and findings where urinary symptoms are not apparently related to any other cause.  |  |

### 4. STUDY DESIGN

This non-randomized, interventional study utilizing a questionnaire-based assessment of men in General Practice. Validation of the tool was performed in a previous GlaxoSmithKline (GSK) study (FDC116700: Quick Question Tool Development and Linguistic Validation). Men who sign the informed consent form and meet the eligibility criteria will be enrolled and complete the Part I diagnostic tests at the GP clinic. If the GP determines that the subject has probable BPH (IPSS  $\geq 8$  and/or BPE/BPO questionnaire  $\geq 3$  with a PSA  $\geq 2$  ng/ml), the subject proceeds to Part II and is scheduled for a urologist assessment and diagnostic tests to confirm or refute a BPH diagnosis and to assess risk of progression of BPH.

#### 4.1. Overall Design

This study is intended to reproduce the circumstances in which the BPH quick tool will be used in General Practice, i.e., in men that may have ‘hidden’ LUTS symptoms. To reproduce these circumstances of opportunistic screening, men will not be invited to attend their GP but **must attend spontaneously with for reasons that are not related to this study**. At this point they will be invited to participate in the study.

GPs participating in the study will recruit men  $\geq 50$  years that present in their clinic for reasons that are not related to this study.

After obtaining informed consent, the GP will initially assess all inclusion and exclusion criteria except for the questionnaire inclusion criterion. If the subject meets those eligibility requirements, the GP administers the BPE/BPO and IPSS screening tools. Subjects who have a positive score on the BPE/BPO screening tool (total score  $\geq 3$ ) and/or the IPSS tool (score  $\geq 8$ ) and meet all other eligibility requirements will be enrolled in Part I of the study. The GP then performs the following diagnostic tests for Part I of the study: urinalysis (sample sent to local lab if the strip test is positive) and Prostate Specific Antigen (PSA) blood test. If the serum PSA result is  $\geq 2$  ng/mL, the GP will make a diagnosis of ‘probable BPH (subjects with symptoms likely to be related to BPH)’ or not. All men with ‘probable BPH’ will proceed to Part II and will be scheduled for Visit 3 with a urologist for confirmation of the GP’s findings plus a brief physical exam and DRE. Additional testing may be performed as per standard of care to assist with a confirmatory diagnosis such as a DRE, however this is not required by the protocol.

The urologist is to:

1) Establish a clinical diagnosis of BPH

AND

2) Estimate whether the patient is at risk of progression of BPH (PSA  $\geq 2.0$  ng/mL and other testing).

For the purposes of this study the diagnosis of the urologist (BPH yes/no) is the operational definition of confirmed BPH. Those men refusing referral to the urologist, but considered by a GP to have BPH (after the tests specified above) will be classified as ‘probable BPH’.

## Description of Visits:

## VISIT 1 (primary care clinic)

- Males  $\geq 50$  years visiting GP for reasons unrelated to the study
- Patient provides informed consent

Eligible to participate

- Inclusion/exclusion criteria confirmation
- Medical history and demography
- BPE/BPO and IPSS screening tools

If subject meets entry criteria, including a positive IPSS (score  $\geq 8$ ) and/or BPE/BPO (score  $\geq 3$ ).

ENROLLED: Subject is enrolled and proceeds to Part I (GP Assessment) of the study. If the GP diagnoses probable BPH, the subject will proceed to Part II (urologist assessment).

[figure not shown]
## PART I: GP Assessment

After being enrolled, complete the following at Visit 1:

- Urinalysis strip test.
  - If strip test is positive, send urine sample to local lab urinalysis.
- PSA blood test
- Additional testing may be performed as per standard of care to assist with a confirmatory diagnosis such as a DRE, however this is not required.

## VISIT 2 (telephone call)

- GP reviews urinalysis and PSA lab results.
- Call subject: If lab results show NO probable BPH, then subject will not continue in the study. If PSA lab results show PROBABLE BPH ( $\geq 2$  ng/mL), subject proceeds to Part II and Visit 3 is scheduled for the urologist assessment.

**VISIT 3 (Part II – urologist clinic visit)**

- Urologist reviews medical history and symptoms
- Brief physical examination
- DRE
- Review previous tests (BPE/BPO screening tool, IPSS screening tool, urinalysis, PSA)

**Urologist provides:**

- Confirmation of clinical diagnosis of BPH (or confirmation the subject does NOT have BPH).
- Estimate whether the patient is at risk of progression of BPH (PSA  $\geq$  2.0ng/mL and other tests).

- NOTE: Urologist may need to perform additional diagnostic testing as per standard of care and as needed to assess the BPH diagnosis. This follow-up is not prescribed by this protocol, however, any data collected that is used for the final diagnosis will be entered in the study case report form (CRF). Advice or treatment post study will be discretion of the GP or Urologist.

**4.2. Treatment Arms and Duration**

- Approximately 1,500 males presenting to a GP for a reason that is not related to this study will be screened for probable BPH to yield 500 subjects being referred to a urologist.
- The duration of the study will be 1 week ( $\pm$  4 days) and up to 6 weeks to allow for GP and urologist visit scheduling.

There is no study drug in this study.

### **4.3. Type and Number of Subjects**

Approximately 1,500 males presenting to a GP for reasons unrelated to this study will be screened for probable BPH to yield 500 subjects being referred to a urologist.

### **4.4. Design Justification**

The BPE/BPO screening tool has been developed using the currently recommended FDA guidelines ([Food and Drug Administration](#), 2009) for developing patient-completed questionnaires such as Patient Reported Outcomes. The tool to be used in this study in the General Practice setting has undergone validation in a urology setting to demonstrate the validity of the tool in populations with and without a definite diagnosis of BPH (GSK Study FDC116700). The FDC116700 study demonstrated that the most effective have been observed by screening patients with BPE/BPO items with a threshold score  $\geq 3$  and then testing such patients with PSA. With total PSA greater than or equal to 2 the combination screener/PSA shows a sensitivity of 83.8% and a specificity of 74.0%, with an accuracy of 80.1%.

### **4.5. Dose Justification**

No investigational study drug will be used in this study.

### **4.6. Benefit:Risk Assessment**

The following section outlines the risk assessment and mitigation strategy for this protocol:

**4.6.1. Risk Assessment**

| Potential Risk of Clinical Significance   | Summary of Data/Rationale for Risk                              | Mitigation Strategy   |
|---|---|---|
| Study Procedures   |   |   |
| Urine strip test  | Routine and minimal risk  | Serious adverse events (SAEs) are monitored via automated emails and adverse events (AEs) are reviewed on a routine basis to identify any procedure related events. |
| PSA blood test:

The risks of taking blood include pain, a bruise at the point where the blood is taken, redness and swelling of the vein and infection, and a rare risk of fainting. | Routine and minimal risk  | SAEs are monitored via automated emails and AEs are reviewed on a routine basis to identify any procedure related events.   |
| DRE:  | Routine and minimal risk. Procedure used in evaluation for BPH. | SAEs are monitored via automated emails and AEs are reviewed on a routine basis to identify any procedure related events.   |
| Urologist physical examination  | Routine and minimal risk. Procedure used in evaluation for BPH. | Performed by a urologist.

SAEs are monitored via automated emails and AEs are reviewed on a routine basis to identify any procedure related events.          |

#### 4.6.2. Benefit Assessment

Subjects could benefit from this study by having the protocol-specified assessments and procedures performed. It is possible that undiagnosed BPH could be identified.

#### 4.6.3. Overall Benefit:Risk Conclusion

Taking into account the measures taken to minimize risk to subjects participating in this study, the potential risks identified in association with the procedures to be performed in this study are justified by the anticipated benefits that may be afforded to subjects who may have undiagnosed BPH.

### 5. SELECTION OF STUDY POPULATION AND WITHDRAWAL CRITERIA

Specific information regarding warnings, precautions, contraindications, adverse events, and other pertinent information on the GSK investigational product or other study treatment that may impact subject eligibility is provided in the Informed Consent Form.

Deviations from inclusion and exclusion criteria are not allowed because they can potentially jeopardize the scientific integrity of the study, regulatory acceptability or subject safety. Therefore, adherence to the criteria as specified in the protocol is essential.

#### 5.1. Inclusion Criteria

A subject will be eligible for inclusion in this study only if all of the following criteria apply:

|  |
|--|
| AGE  |
| 1. Greater than or equal to 50 ( $\geq 50$ ) years of age at the time of signing the informed consent form.  |
| SEX  |
| 2. Male  |
| INFORMED CONSENT   |
| 3. Capable of giving signed informed consent as described in Section 9.2 which includes compliance with the requirements and restrictions listed in the consent form and in this protocol. |
| OTHER  |
| 4. Present in a General Practice setting for a reason unrelated to this study.   |
| 5. Positive IPSS score ( $\geq 8$ ) and/or positive BPE/BPO screening tool score ( $\geq 3$ ).   |

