# 1. PROTOCOL SYNOPSIS FOR STUDY FDC116114

## Rationale

The rationale for developing an instrument to screen populations of men for lower urinary tract symptoms (LUTS) due to benign prostatic hyperplasia (BPH) is that it may help a General Practitioners (GP) to identify patients who may have BPH for further tests and improve the speed of referrals to specialists when this is appropriate. Symptomatic BPH is present in 40 – 60% of men over the age of 50 and prevalence rises with age. It is known that men with LUTS may be reluctant to discuss these symptoms with their GP, and that GPs do not routinely proactively ask about LUTS when men present for other complaints. As a result, many men with BPH present late with more severe symptoms. As a result up to 70% of men may have moderate to severe BPH at their initial diagnosis. The recent D-IMPACT study confirmed that GPs can accurately diagnose BPH in around 75% of men presenting with LUTS, using simple tests. A Benign Prostatic Enlargement (BPE)/Benign Prostatic Obstruction (BPO) screening tool which identifies LUTS probably due to BPH in men not yet presenting with LUTS would provide an opportunity to proactively assess men who do not present with LUTS. BPH is a progressive condition and identifying men at risk of progression is important to allow their treatment to be optimised. Furthermore the utility of the screening tool will be compared to the validated tool in wide clinical use, the International Prostate Symptom Score (IPSS).

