## Treatment Arms and Duration

- Approximately 1,500 males presenting to a GP with a primary complaint other than LUTS will be screened for probable BPH to yield 500 subjects being referred to a urologist.
- The duration of the study will be 1 week ( $\pm 4$  days) and up to 6 weeks to allow for GP and urologist visit scheduling.
- There is no study drug in this study.

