### 2.1. Study Rationale

The rationale for developing an instrument to screen populations of men for lower urinary tract symptoms (LUTS) due to BPH is that it may help a GP to identify patients who may have BPH for further tests and improve the speed of referrals to specialists when this is appropriate. Symptomatic BPH is present in 40 – 60% of men over the age of 50 and prevalence rises with age (Emberton, 2003). It is known that men with lower urinary tract symptoms (LUTS) may be reluctant to discuss these symptoms with their GP, and that GPs do not routinely proactively ask about LUTS when men present for other complaints. As a result, many men with BPH present late with more severe symptoms. As a result, up to 70% of men may have moderate to severe BPH at their initial diagnosis. The recent D-IMPACT study confirmed that GPs can accurately

diagnose BPH in around 75% of men presenting with LUTS, using simple tests (Carballido, 2011). A simple screening tool which identifies LUTS probably due to BPH in men not yet presenting with LUTS would provide an opportunity to proactively identify and potentially treat men who do not present with LUTS as their primary complaint. It is important to identify BPH early. BPH is a progressive condition and identifying men at risk of progression is important to allow their treatment to be optimised (Fitzpatrick, 2006). Furthermore the utility of screening tool will be compared to a validated tool in wide clinical use, the International Prostate Symptom Score (IPSS).

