### CONCURRENT CONDITIONS/MEDICAL HISTORY (INCLUDES LIVER FUNCTION AND QTc INTERVAL)

1. History of BPH for which they have received test procedures, medical intervention and/or medicine.
2. History of prostate-related LUTS for which they have received test procedures, medical intervention and/or medicine.
3. History of prostatic surgery (including transurethral resection of the prostate [TURP], balloon dilatation, thermotherapy, and/or stent replacement) or other invasive or minimally invasive procedures to treat BPH.
4. Has other conditions that may cause urinary symptoms (e.g., neurogenic bladder, bladder neck contracture, urethral stricture, bladder malignancy, acute or chronic prostatitis, or acute or chronic urinary tract infections, etc.).
5. History or evidence of prostate cancer (e.g., positive biopsy or ultrasound, suspicious DRE and/or rising PSA).

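### Inclusion criterion 4 is looser than the stated target population: read literally, it admits men visiting the GP about LUTS, which could inflate the primary proportion

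*Protocol*

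**What the plan says.** The documents describe the population in two ways.

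**Looser: the visit is not connected with the study.** Criterion 4 in Protocol Section 5.1 reads "Present in a General Practice setting for a reason unrelated to this study". The same test appears in Section 4.1 (text and Visit 1 description) and in Sections 4.2 and 4.3. It is also in the synopsis under Type and Number of Subjects and under Analysis, and in the SAP in Section 1 (Study Design) and Section 2.3 (Visit 1).

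**Narrower: LUTS is not the main reason for coming.** The synopsis, under Treatment Arms and Duration, says "males presenting to a GP with a primary complaint other than LUTS will be screened for probable BPH". SAP Section 2.3, under Treatment Assignment, has the same wording. The synopsis Rationale wants a tool that "identifies LUTS probably due to BPH in men not yet presenting with LUTS". Section 2.1 aims to "proactively identify and potentially treat men who do not present with LUTS as their primary complaint". Section 4.1 says the tool is meant for use "in men that may have ‘hidden’ LUTS symptoms".

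The exclusion nearest to the point is "History of prostate-related LUTS for which they have received test procedures, medical intervention and/or medicine". A parallel exclusion covers BPH already tested or treated. Others cover conditions that may cause urinary symptoms, and a history or evidence of prostate cancer.

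**The concern.** Section 5 of the protocol allows no deviation from the eligibility criteria, so sites work from criterion 4 and not from the synopsis. Taken at its word, the criterion is met by almost any spontaneous visit, including a first consultation about urinary symptoms. A site that enrolled such a man would comply with Section 5.1 and contradict the synopsis, and no protocol deviation would arise.

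The primary endpoint is the proportion with urologist-confirmed BPH among men with a BPE/BPO score of at least 3 and PSA of at least 2 ng/mL. It is a positive predictive value, so it rises with the frequency of BPH among the men screened. Men who come because of LUTS plausibly have more BPH than men with unreported symptoms. Including them would push the estimate up and away from the group the study asks about. If sites or countries read the phrase differently, the planned proportions by country and center would also differ for that reason alone.

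**Working it through.** **1. Can the plan remove or identify such men?**

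- Exclusions (Protocol 5.2): a man with untested, untreated LUTS, no other known urinary cause and no evidence of prostate cancer is not excluded.
- Primary denominator (Protocol 8.4.2, SAP 7.1.2): no condition on the reason for visit.
- Time and Events table (Protocol 6.1): no reason-for-visit item. SAP 6.5 summarises urinary conditions from the medical history, but a history of symptoms does not show why the man came.
- Subgroups (SAP Appendix 11): country and center only.
- Sensitivity analyses of the primary endpoint (SAP 7.1.2): entered as not applicable.

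**2. The plan's own precision figure (Protocol 8.2).** Half-width = 1.96 × √(0.5 × 0.5 / n).

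- n = 300: 0.0566 (stated 0.057)
- n = 500: 0.0438 (stated 0.044)
- n = 700: 0.0370 (stated 0.037)

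All three reproduce. The expected yield also agrees: 0.33 × 1,500 = 495, about 500. The sample-size figures are not at issue.

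**3. Illustrative size of the shift.** Inputs from the documents are sensitivity 0.838 and specificity 0.740 for screener plus PSA (Protocol 4.4, from a urology setting), and symptomatic BPH in 40-60% of men over 50 (Protocol 2.1). Two inputs are assumptions: LUTS visits as a share f of screened men, 5-30%; and BPH frequency among those men, 75-90%.

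PPV(p) = 0.838p / [0.838p + 0.260(1 − p)], with p = f × p(LUTS) + (1 − f) × p(target).

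PPV is 0.682, 0.763, 0.829, 0.906 and 0.967 at p = 0.40, 0.50, 0.60, 0.75 and 0.90.

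Worked case: p(target) = 0.40, p(LUTS) = 0.75, f = 0.20. Then p = 0.15 + 0.32 = 0.47, and PPV = 0.39386 / (0.39386 + 0.1378) = 0.741. Against 0.682 the shift is 0.058.

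Shift in the primary proportion, by p(target) / p(LUTS):

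| f | 0.40 / 0.75 | 0.40 / 0.90 | 0.50 / 0.75 | 0.50 / 0.90 | 0.60 / 0.75 | 0.60 / 0.90 |
|---|---|---|---|---|---|---|
| 5% | 0.0155 | 0.0219 | 0.0089 | 0.0142 | 0.0044 | 0.0088 |
| 10% | 0.0304 | 0.0426 | 0.0176 | 0.0277 | 0.0088 | 0.0173 |
| 20% | 0.0584 | 0.0808 | 0.0343 | 0.0533 | 0.0173 | 0.0336 |
| 30% | 0.0844 | 0.1151 | 0.0502 | 0.0770 | 0.0255 | 0.0491 |

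Every entry at 5% and 10% is below 0.0438. That figure is the maximum, reached at a proportion of 0.50. In the least favourable 10% cell the observed proportion would be 0.725, where the half-width at n = 500 is 1.96 × √(0.725 × 0.275 / 500) = 0.039, slightly below the shift of 0.0426.

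**4. A simpler cross-check.** Put the planning value of 0.50 for target men and an assumed 0.75 for LUTS visitors directly into the primary denominator. The shift is 0.25f, with f now a share of that denominator: 0.025 at 10% and 0.075 at 30%. It reaches 0.044 at f = 0.044 / 0.25 = 0.176, about 18%.

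**5. Precision if LUTS visitors are removed from the 500.** The maximum half-width becomes 0.045 (n = 475, 5% removed), 0.046 (n = 450, 10%), 0.049 (n = 400, 20%) or 0.052 (n = 350, 30%).

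**The case against.** The strongest reply is that the literal reading was never intended. Protocol Section 2.2 uses the same phrase about reasons unrelated to the study when it speaks of reaching men who might not think of consulting about these symptoms. There it evidently means a visit not about LUTS. The rationale for Amendment 1 describes urine and blood sampling as outside normal practice for men attending for unrelated reasons, which fits poorly with a group that includes LUTS visits. The title refers to men presenting with other co-morbidities. A sensible GP might therefore exclude LUTS visits without being told.

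This stands as evidence of intent, and it makes the problem one of ambiguity. It does not settle the matter, because Section 4.1 stresses that men are not invited to attend, which supports the literal reading. The synopsis also shows that clearer wording was available.

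Three further limits stand. The exclusions for other urinary causes and for prostate cancer remove some men who would consult about urinary symptoms. The primary analysis is descriptive, so no test result can change. The eCRF is not among the documents, so it cannot be confirmed that the reason for visit goes unrecorded.

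A reader might infer that the synopsis and SAP consistently define the narrower population. They do not: each uses both wordings. A reader might also take the figure of around 75% in Section 2.1 as BPH prevalence among men with LUTS. It describes how often GPs diagnose correctly.

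**Conclusion.** The population definition is inconsistent, and the binding criterion carries the looser version. A site following it literally could enrol men outside the stated target without a recorded deviation, and nothing in the protocol or SAP would later separate them.

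The likely direction is upward. The size is unknown: about 0.4 to 11.5 points over the assumed ranges, within the stated maximum half-width at shares of 10% or less, and beyond it only with a larger share and a clear contrast in BPH frequency. A 20% share at 75% BPH adds 5.8 points if target prevalence is 40%, but 1.7 points if it is 60%. These figures also assume that sensitivity and specificity from a urology setting carry over to general practice and are equal in both groups of men.

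The documents do not support the stronger inference that the primary proportion will be materially inflated or that criterion 4 is plainly wrong. They give neither the share of LUTS visits nor the BPH frequency among them, and the 0.50 in the sample-size section is a conservative planning value, not an expected rate. This is a cheap improvement: an inconsistency to reconcile.

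**What to change.** Reword criterion 4 so that it requires both conditions: "presenting to a GP with a primary complaint other than LUTS", and a visit unrelated to the study. Bring the looser passages into line: synopsis (Type and Number of Subjects; Analysis), Protocol Sections 4.1 (including the Visit 1 description), 4.2 and 4.3, and SAP Sections 1 and 2.3. Record the reason for visit on the CRF if it is not already there. Add to SAP Section 7.1.2 a sensitivity estimate of the primary proportion, with its 95% confidence interval, excluding any LUTS visits.

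The reworded criterion would still admit men who raise LUTS as a secondary complaint. That agrees with Section 2.1, and the new CRF item would let their number be reported.

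The cost is wording, one CRF field and one extra table. Eligible numbers fall in proportion to the share of LUTS visits: the maximum half-width rises from 0.044 to 0.045-0.046 if 5-10% of the 500 are lost, and to 0.052 if 30% are lost, unless more men are screened.
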